7.4.3 Subject Death

Subject death will be treated the same as lost to follow-up, including imputation of missing data. The notable exception is the binary primary efficacy endpoint for seizure freedom: If a subject death after the Visualase procedure has been determined to be seizure-related via the Adverse Event reporting process, the subject may not be imputed as seizure free. Note that Sudden Unexpected Death in Epilepsy (SUDEP) may or may not be seizure-related.

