7.17 Retreatment

Subjects who fail to achieve Engel Class I seizure freedom or whose procedure could not be completed as intended prior to discharge may be evaluated for retreatment. Retreatment is defined as a subsequent Visualase procedure after the subject's discharge following the initial Visualase procedure, to treat MTLE ipsilateral to the initial Visualase procedure and also within the temporal lobe. If it is determined that the ablation of additional tissue within the original target site may improve the outcome, the

justification for retreatment and supporting evidence will be entered on an eCRF and submitted to the Pre-Surgical Evaluation Committee for assessment per Section 7.12. Justification and supporting evidence for consideration of retreatment may include, but is not limited to, EEG demonstrating interictal and ictal discharges from the same temporal lobe, MRI showing no other lesions, same type of seizure behavior and auras, and no evidence of extra-temporal lesions.

If the Pre-Surgical Evaluation Committee disagrees with the recommendation for retreatment, the subject may continue participation in the study per their original follow-up schedule without retreatment. Alternatively, the subject may be withdrawn from the study.

If the committee agrees with the recommendation for retreatment, the subject may be scheduled for an additional Visualase procedure. Retreated subjects will have the same assessments at the same intervals as they would for an initial procedure. The new follow-up visit windows will be calculated based on the date of the retreatment Visualase procedure.

Subjects retreated with Visualase after the subject's discharge from the original Visualase procedure will be considered to have failed the primary efficacy endpoint. However, their data will contribute to specified secondary endpoints.

Subjects who undergo open resection after a Visualase procedure will be considered to have failed the primary efficacy endpoint. Seizure and AE data will be collected per the standard of care for the site.

Subjects who are retreated with Visualase or undergo open resection after a Visualase procedure will be followed for 12 months after the secondary procedure, or until the last enrolled subject completes Follow-up Visit 4 (12 months), whichever occurs first.

All subjects will be assessed for safety for the duration of their participation in this study, regardless of whether they are retreated.

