10.2 Adverse Event and Device Deficiency Assessment

10.2.1 Study Reportable Adverse Events

Adverse event definitions are provided in Table 6. To ensure all AEs that are potentially relevant to the SLATE study are collected, the following adverse events will be collected and reported to Medtronic during the study, starting from the time the subject signs the informed consent:

- Device-related AEs
- Procedure-related AEs
- Anesthesia-related AEs
- Epilepsy-related AEs
- All SAEs

Each AE must be recorded on a separate AE eCRF and include a description of the event, the diagnosis, date of event onset, the date the site became aware of the event, diagnostic tests and procedures performed, actions taken as a result of the event, relatedness and severity of the event and the outcome of the event. Subject deaths are also required to be reported. Refer to Section 10.5 for subject death collection and reporting requirements.

Documented pre-existing conditions are not considered AEs unless the nature or severity of the condition has worsened. Unavoidable events listed in Table 6 need not be reported unless the AE worsens or is present outside the stated timeframe post-procedure.

Seizures are inherent to the disease state of the target population of this study and are expected to continue in a portion of subjects after the Visualase procedure. While all seizures will be reported and captured in a seizure diary, they will not be reported as AEs unless there is a worsening in the nature, severity or degree of incidence, according to the Investigator's opinion. Following are examples of seizures that are reportable as AEs:

- Worsening in clinical manifestations (for example, subject began having falls with their seizures which was not previously a component)
- Seizure frequency is increased
- Subject experiences a new seizure type or non-epileptic seizure
- Seizure led to injury or death

Memory and naming decline are established risks following epilepsy surgery involving the temporal lobe. In standard ATL resections, changes in these cognitive scores are expected and consequently are not considered as adverse events unless the magnitude of change exceeds the site investigator's expectations.

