10.3 Adverse Event Classification and Device Deficiency Review and Reporting

All AEs and device deficiencies will be reviewed by a Medtronic representative for completeness and accuracy and will request clarification and/or additional information from the Investigator when necessary.

Adverse events will be classified according to the definitions provided in Table 6.

Medtronic will utilize MedDRA, the Medical Dictionary for Regulatory Activities, to assign a MedDRA term for each AE based on the information provided by the Investigator.

Regulatory reporting of AEs will be completed according to FDA requirements. Refer to Section 10.4 for a list of required Investigator and Medtronic reporting requirements and timeframes. It is the responsibility of the Investigator to abide by any additional AE reporting requirements stipulated by the IRB responsible for oversight of the study.

Appendix E contains the Foreseeable Adverse Event List (FAL), which is a list of AEs related to the system or procedure that have been observed in previous relevant

(epilepsy) studies and may be experienced by subjects. This list may help to assess if an AE is unexpected in nature.

For emergency contact regarding a UADE, SAE and/or SADE, contact a clinical study representative immediately (refer to the study contact list provided in the site's study documents binder/investigator site file or refer to the contact information provided in this CIP).

AEs and deaths will be classified according to the responsibilities and parameters outlined in Table 7 below.

Table 7: Adverse Event Classification Responsibilities

What is Classified?	Who Classifies?	Classification Parameters	
Timing of the Event	Investigator	Pre-operative, intra-operative or post-operative	
Relatedness	Investigator	Procedure Anesthesia Device (Visualase System) Epilepsy	
	Sponsor	Procedure Anesthesia Device (Visualase System) Epilepsy	
	Investigator	Serious adverse event	
Seriousness	Sponsor	Serious adverse event Unanticipated adverse device effect	
Carranita .	Investigator	Mild, moderate, or severe	
Severity	Sponsor	Mild, moderate, or severe	
Diagnosis	Investigator	Based on presenting signs and symptoms and other supporting data	
	Sponsor	MedDRA term assigned based on the data provided by Investigator	
Death Classification	Investigator	SUDEP	

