10.5 Subject Death

The AE that led to the subject death must be documented on an Adverse Event form as soon as possible after the Investigator first learns of the death. A study exit eCRF must also be completed.

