7.4 Handling of Missing, Unused, and Spurious Data and Dropouts

7.4.1 Missing Data

Missing primary efficacy endpoint values and missing secondary endpoint values associated with testable hypotheses will be imputed for analysis with the mITT analysis population. Missing primary efficacy endpoint data will be imputed as a binary outcome of seizure freedom, regardless of missing pattern. No daily level imputation will be conducted.

The primary method of imputation will be multiple imputation (SAS PROC MI followed by MIANALIZE). Ten repetitions will be performed and, if needed, will be increased until the algorithm converges.

The Markov chain Monte Carlo (MCMC) method or Fully Conditional Specification (FCS) will be used with the default number of burn-in iterations before the imputation. The model variables will include: age, sex, race (white, African American, or other), and duration of disease.

SLATE Statistical Analysis Plan		Form
Revision 1.0	Page 10 of 23	Medtronic

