7.5 Adjustments for Multiple Comparisons

Secondary endpoints will be tested only if the primary efficacy endpoint is significant. Secondary endpoints will be tested in a hierarchical fashion to preserve alpha. Each secondary endpoint will be tested at alpha 0.05, but testing will stop when any secondary endpoint fails to achieve significance.

Secondary Endpoints #1, 2 and 8 are not truly independent secondary endpoints; rather they are secondary analyses of the primary efficacy endpoint. To maintain the hierarchical approach for testing the hypotheses and for consistency with the Clinical Investigational Plan, these secondary analyses of the primary endpoint are considered secondary endpoints in this section.

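### A death caused by the device, procedure or anesthesia is imputed for the primary efficacy endpoint and can add a fraction of a success to the seizure-free rate

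*SAP*

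**What the plan says.** SAP 7.4.3 sets the general rule: "Subject death will be treated the same as lost to follow-up, including imputation of missing data". For the binary primary efficacy endpoint it makes one exception: a subject whose death after the procedure is found, through adverse event reporting, to be seizure-related may not be imputed as seizure free. It adds: "Note that Sudden Unexpected Death in Epilepsy (SUDEP) may or may not be seizure-related".

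SAP 7.4.1 describes the imputation: "Missing primary efficacy endpoint data will be imputed as a binary outcome of seizure freedom, regardless of missing pattern". The listed model variables are age, sex, race and duration of disease, with ten repetitions, more if needed. Death and its cause are not listed.

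The modified intent-to-treat set starts at scalp incision (SAP 7.1.3.2), so intra-operative and post-operative deaths are in the denominator. The outcome window runs from day 30 to day 365 (SAP 7.9.2).

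Protocol 7.17 takes the other course for two further events. Retreatment after discharge is a failure, and so is resection: "Subjects who undergo open resection after a Visualase procedure will be considered to have failed the primary efficacy endpoint".

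On classification, Protocol 10.3 says "AEs and deaths will be classified according to the responsibilities and parameters outlined in Table 7 below". Table 7 records relatedness to procedure, anesthesia, device and epilepsy, and SUDEP for deaths.

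**The concern.** The primary hypothesis concerns the proportion of treated subjects who are seizure free at 12 months. A subject killed by the treatment is not an unobserved visit; the outcome is known, and it is not survival free of seizures. Under SAP 7.4.3 that subject is nevertheless given a yes/no outcome drawn at about the survivors' rate. Someone who dies of a procedural complication on day 5, before the outcome window opens, is handled like someone who moved away.

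The plan is also uneven. Needing a second ablation or a resection is a failure, while dying of the first ablation is a partial success on average. The study has one arm and a fixed threshold, so no comparator offsets the credit. At stake are a few tenths of a percentage point per death and, for a result close to the threshold, the decision itself.

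The point is limited to deaths before day 365 in subjects without an earlier failing event (a disabling seizure after day 30, retreatment or resection).

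**Working it through.** **Inputs.** From SAP section 6: N = 150 treated, threshold 43%, expected rate 56%, success if the lower limit of the two-sided exact 95% interval exceeds 43%, stated power 89%. Assumption: d = 1, 2 or 3 treatment-related deaths among the 150.

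**Step 1: reproduce the plan's figure.** Exact (Clopper-Pearson) lower limits for n = 150:
- 76/150 gives 42.39% (fails)
- 77/150 gives 43.05% (passes)

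The limit equals 43% at a count of 76.93. Requiring at least 77, the error at 43% is 2.44% and the power at 56% is 89.1%, which agrees with the stated 89%.

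**Step 2: credit per death.** At 56%, 0.56/150 = 0.37 percentage points; at 43%, 0.43/150 = 0.29.

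**Step 3: the pass rule.** Let s be the seizure-free survivors. With deaths as failures, s ≥ 77 is needed for every d. With imputation at the survivors' rate the mean count is s × 150/(150 − d). For s = 76:
- d = 1: 76 × 150/149 = 76.51, below 76.93, fails
- d = 2: 76 × 150/148 = 77.03, passes
- d = 3: 76 × 150/147 = 77.55, passes

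**Step 4: ten random imputations instead of the mean.** Let K be the number of imputed successes over ten draws of d subjects. Averaging the counts, 76 survivors pass if 76 + K/10 ≥ 76.93, that is K ≥ 10.
- d = 1: all ten draws must be successes, (76/149)^10 = about 0.1%
- d = 2: K is binomial(20, 76/148), so about 63% of runs pass
- d = 3: K is binomial(30, 76/147), so about 99% of runs pass

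The SAP does not say how the exact interval is pooled over imputations. Across the pooling methods tried, the pass share at 76 was about 48-64% for d = 2 and 95-99% for d = 3.

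**Step 5: one-sided error if 43% counts deaths as failures.** The survivor rate at the null is then 0.43 × 150/(150 − d), or 43.58% for d = 2 and 43.88% for d = 3.

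| d | Deaths as failures | Mean count | Ten imputations |
|---|---|---|---|
| 1 | 2.40% | 2.40% | 2.4% |
| 2 | 2.37% | 3.46% | about 3.0-3.1% |
| 3 | 2.34% | 3.42% | about 3.4-3.5% |

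For example, with d = 2: P(s ≥ 77) = 2.37%, P(s = 76) = 1.08%, and 2.37 + 0.63 × 1.08 = 3.05%. At the low end of the pooling range, 2.37 + 0.48 × 1.08 = 2.89%.

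**Step 6: one-sided error if 43% is the survivors' rate.** Imputed by mean count: 2.49% (d = 2) and 2.07% (d = 3), so no excess. Deaths as failures: 1.7% and 1.4%, which is conservative.

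**Step 7: power at a 56% survivor rate.**

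| d | Deaths as failures | Mean count | Ten imputations |
|---|---|---|---|
| 1 | 87.4% | 87.4% | 87.4% |
| 2 | 85.5% | 88.9% | about 87-88% |
| 3 | 83.3% | 87.1% | about 87% |

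The decision turns almost entirely on s = 76, which has probability 3.4% (d = 2) or 3.8% (d = 3) at 56%.

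**The case against.** The best defense is that this is a choice of estimand. The SAP addresses death expressly, and the study has separate thresholds for efficacy (43%) and safety (40%). A related death that meets the qualifying rules counts against the safety endpoint (Protocol Appendix F, SAP Appendix 2). Nothing in the documents says that the 43% benchmark counts deaths as failures. That stands as a limit on the claim of excess error. It does not remove the efficacy credit, because a safety count does not cancel a success in another endpoint.

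The practical effect is also remote: at least two such deaths and a result at the boundary. The summary of 37 published patients in Protocol 3.2 lists no deaths. This bears on size, not on whether the rule is sound.

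A reader might infer more than the documents support:
- *That every SUDEP should be a failure.* The SAP deals with SUDEP expressly, and Protocol Table 6 allows that there may be no evidence of a seizure near death. Failing all of them is a preference; a sensitivity analysis is enough.
- *That seizure deaths slip through because Table 7 has no seizure-related category.* Protocol 10.2.1 lists "Seizure led to injury or death" among reportable seizures, and Protocol 10.5 says "The AE that led to the subject death must be documented on an Adverse Event form as soon as possible". The exception can be applied.
- *That the exception plainly reaches secondary endpoints 1 and 8.* SAP 7.5 says of endpoints 1, 2 and 8 that "rather they are secondary analyses of the primary efficacy endpoint", but that section concerns multiplicity. Carrying the death rule across is an inference and should be written down.
- *That endpoint 2 is wholly open.* Retreated subjects who do not reach 12 months after retreatment already count as not seizure free (Protocol 14.6.2, SAP 7.9.3.2). Only non-retreated subjects remain.
- *That no sensitivity analysis exists.* SAP 7.4.2 is not in the public text and may contain one.

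**Conclusion.** The point holds for device-, procedure- and anesthesia-related deaths before day 365 in subjects with no earlier failing event. SAP 7.4.3 imputes them, the listed model variables ignore the death, and Protocol 7.17 treats lesser events as failures.

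The size is small: at most about 0.37 points per death at 56%, and essentially no change in the decision with one death. With two or three deaths the one-sided error rises by about 0.6-0.7 points (3.0-3.1% against 2.4%) or 1.1-1.2 points (3.4-3.5% against 2.3%), on the reading that 43% counts deaths as failures. On the other reading there is no excess, so a flat statement that the type I error is inflated goes further than the documents allow.

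These figures assume 1 to 3 deaths, imputation at about the survivors' rate with no covariate effect, and a pooling method that the SAP leaves open. The change should be made because it is nearly free and is best settled before database lock, not because the result is likely to hinge on it.

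**What to change.** In SAP 7.4.3, count as not seizure free any death from scalp incision through day 365 that is classed as device-, procedure- or anesthesia-related under the existing Table 7 categories, alongside seizure-related deaths. State that this applies to the primary efficacy endpoint, to secondary endpoints 1 and 8, and to non-retreated subjects in secondary endpoint 2.

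Keep imputation for other deaths. In a sensitivity analysis, report SUDEP not judged seizure-related, and deaths of other or unknown cause, both imputed and as failures. If SAP 7.4.2 already contains this analysis, a cross-reference is enough.

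Cost: one or two sentences and no new data. If such deaths occur, the rate falls by about 0.37 points per death at 56%. Power falls from about 87-88% to 85.5% with two, or from about 87% to 83.3% with three, and is essentially unchanged with one. If 43% is really a survivors' rate, the test becomes conservative (1.7% or 1.4% one-sided error).

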11 RISK ANALYSIS

Medtronic follows rigorous Quality Assurance and Control procedures throughout the life of a product, from the business analysis phase through development, market release, and post-market surveillance. The risk analysis process for the SLATE study was performed to ensure that the level of risk is acceptable prior to starting the clinical study.

Possible risks of the Visualase procedure in this study include, but are not limited to, the foreseeable adverse events listed in Appendix E. There may be other discomforts and risks related to the Visualase device and/or this study that are not foreseen at this time.

There is a possibility of risks to an unborn child. These risks are unknown. Women who are pregnant at the time of the procedure or plan to become pregnant during the course of the study are excluded from participating.

Possible additional risks associated with participation in the SLATE study include, but are not limited to, the following:

- Ineffective treatment:
 - Risks associated with continued seizures, including injury and sudden unexpected death in epilepsy (SUDEP)
- Neuropsychological testing:
 - o Mild emotional stress
 - Embarrassment or unpleasant feelings
 - Mild emotional discomfort due to personal questions about mood or behavior
- Research MRI:
 - Bothersome MRI machine noise
 - Feelings of claustrophobia
 - Injury if objects containing iron or metal are present in the subject or anywhere in the room
- Research MRI contrast agent (gadolinium):
 - Discomfort

- Tingling or warmth in the lips
- Metallic taste in the mouth
- Tingling in the arm
- Nausea
- Headache
- Allergic reaction to gadolinium
- Visual field exam
 - Fatigue
- Neuro-ophthalmologic exam dilating eye drops
 - Stinging
 - o Blurry vision
 - Sensitivity to light
 - Allergic reaction

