7.9.3 Secondary Endpoints

All secondary endpoints have specific hypotheses to be tested. The hypotheses associated with each of these secondary endpoints will be tested in a hierarchical fashion. If the primary efficacy endpoint is not significant, then no secondary endpoints will be tested. Testing of these secondary endpoints will proceed in the following order using an alpha of 0.05 and will stop if any test fails to reach significance.

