7.9.3.5 Secondary Endpoint #5

Within-subject change of the Quality of Life in Epilepsy inventory (QOLIE-31) score (English language version), from baseline to 12 months following the Visualase procedure, categorized as -1 if the decrease is clinically significant (\leq -11.8), categorized as 0 if not clinically significant (-11.7 to +11.7), and categorized as +1 if the increase is clinically significant (\geq 11.8).

It is hypothesized that the QOLIE-31 score will increase (improve) from baseline to 12 months following the Visualase procedure. The hypotheses associated with this endpoint are as follows:

Null Hypothesis: M (V-QOLIE-31 - BSL-QOLIE-31) \leq 0 Alternate Hypothesis: M (V-QOLIE-31 - BSL-QOLIE-31) > 0

Where M (V-QOLIE-31 - BSL-QOLIE-31) = sign-test statistic ([increases-decreases]/2) in the Quality of Life in Epilepsy inventory from baseline to Month 12 post Visualase.

A sign test will be used to determine if the median categorical change is significantly greater than zero. The Minimally Clinically Important Difference (MCID) of 11.8 points for the QOLIE-31 is based on published literature (Wiebe 2002).

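### SAP 7.4.3 imputes 12-month cognitive and quality-of-life results for subjects who have died, so a death can count as an improvement in secondary endpoints 5 to 7

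*SAP*

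**What the plan says.** SAP 7.4.3 sets the general rule: "Subject death will be treated the same as lost to follow-up, including imputation of missing data". It then limits the departure from that rule: "The notable exception is the binary primary efficacy endpoint for seizure freedom". When a death after the procedure is judged seizure-related, "the subject may not be imputed as seizure free". No other endpoint is named.

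SAP 7.4.1 defines what is imputed: "Missing primary efficacy endpoint values and missing secondary endpoint values associated with testable hypotheses will be imputed for analysis with the mITT analysis population". SAP 7.9.3 makes that cover all eight secondary endpoints: "All secondary endpoints have specific hypotheses to be tested". The imputation variables listed in SAP 7.4.1 are age, sex, race and duration of disease, with ten repetitions to start. Protocol 14.3.2 limits imputation of the cognitive and quality-of-life endpoints to the English-language subset but does not take deaths out.

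Endpoints 5 to 7 (QOLIE-31, SF-36 MCS, SF-36 PCS) reduce each subject's change to -1, 0 or +1 and apply a sign test. For QOLIE-31 a subject is "categorized as +1 if the increase is clinically significant", meaning 11.8 points or more. The cut-offs are 4.58 for the MCS and 3.02 for the PCS. Endpoints 3 and 4 (Boston Naming Test, RAVLT) are paired t-tests of mean change against non-inferiority margins.

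**The concern.** A subject who is alive but skips the month 12 questionnaire has a score that was not recorded. A subject who has died has no month 12 score at all. Imputing one gives the dead subject the outcome of a living subject of similar age, sex, race and disease duration. Death itself does not inform the draw, because no death indicator is among the listed variables.

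For endpoints 5 to 7, the worst possible outcome therefore enters as an average one, and in some imputed data sets as a clinically significant gain. The plan is also uneven. It bars a seizure-related death from success on the primary endpoint, yet the same subject may be +1 on QOLIE-31. Deaths are foreseen: Protocol section 11 names SUDEP among the risks of continued seizures, and Protocol Appendix E lists death among the foreseeable events. Endpoints 5 to 7 are successive steps in a fixed testing sequence, so the handling of deaths on one step also affects whether the next is reached.

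**Working it through.** **Does the rule reach endpoints 5 to 7?** SAP 7.4.3 sends deaths to imputation. SAP 7.4.1 imputes every secondary endpoint with a testable hypothesis, and SAP 7.9.3 says all of them have one. The exception in 7.4.3 names only the primary endpoint. No readable text gives a death a fixed category, or excludes it, for endpoints 3 to 7. The rule applies.

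**The plan's own figures.** The plan gives no figure for the effect of deaths. Its subset sizes in SAP section 6 do reproduce: 0.73 × 150 = 109.5 (stated as 109), and half of that is about 55. The cap of 40% on Spanish-language enrolment leaves 0.60 × 150 = 90 English-language subjects, if the cap is reached and the treated share matches the enrolled share. Because mITT values are imputed rather than discarded, 90 is the more suitable size here.

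**How often would a death be imputed as +1?** Assume the QOLIE-31 change in survivors is normal with mean m and SD s. Then P(+1) = 1 − Φ((11.8 − m)/s). The documents give neither m nor s.

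- m = 0, s = 10: 1 − Φ(1.18) = 0.12
- m = 15, s = 10: 1 − Φ(−0.32) = 0.63

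Over m from 0 to 15 and s from 10 to 20 the range is 0.12 to 0.63, or about 1 to 6 of the 10 imputed data sets per death.

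**Effect on the sign test.** Assume 35% of survivors at +1, 15% at −1 and the rest at 0, and a two-sided exact sign test at 0.05 on the non-zero values that passes only if increases exceed decreases. Each death contributes on average to increases minus decreases:

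- SAP rule: 0.35 − 0.15 = +0.20
- death excluded: 0
- death scored −1: −1

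The chance of passing is the sum, over the trinomial distribution of (increases U, decreases D), of the outcomes with U > D and 2·P(Bin(U + D, 0.5) ≥ U) ≤ 0.05. Under the SAP rule all N subjects are drawn. Under exclusion N minus the deaths are drawn. Under the −1 rule the deaths are added to D. One completed data set is used; pooling across imputations is not modelled.

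| N | Deaths | SAP rule | Deaths excluded | Death = −1 |
|---|---|---|---|---|
| 90 | 1 | 74% | 73% | 67% |
| 90 | 3 | 74% | 72% | 52% |
| 55 | 1 | 48% | 47% | 38% |
| 55 | 3 | 48% | 46% | 19% |

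For N = 90 and three deaths, imputing rather than excluding accounts for 74 − 72 = 2 points, and scoring death as −1 rather than excluding it for 72 − 52 = 20 points.

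**Check under no effect.** With 25% improving and 25% declining, the chance of a favourable pass is about 1.5% (N = 55) or 1.8% (N = 90), whether deaths are imputed or excluded.

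**A borderline result.** Take 33 improvers and 16 decliners: p = 0.021. If one, two or three of those improvers were deaths imputed as +1, recoding them to −1 gives p = 0.044, 0.085 and 0.152.

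**The case against.** The SAP rule is explicit and prespecified. The large contrasts above arise only against one alternative, scoring death as −1, which is one of several defensible choices. Against plain exclusion the rule gains about 0.5 to 3 points. A reader might infer that imputing deaths inflates false positives on endpoints 5 to 7 or wrongly opens later steps of the sequence. The calculations do not support that: when survivors improve and decline equally, the pass rate is the same with deaths imputed or excluded. This part of the objection stands.

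The size assumptions also lean high. Three deaths are 3.3% of 90, or 5.5% of 55. The published Visualase reports of 37 patients summarised in Protocol 3.2 list complications but no death. N = 55 comes from a worst case in which missing data are discarded, which is not what the mITT analysis does.

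A reader might also infer that a never-retreated subject with a seizure-related death fails the primary endpoint but may be imputed seizure free on endpoint 2. SAP 7.5 answers most of this by describing endpoints 1, 2 and 8 as secondary analyses of the primary efficacy endpoint, so the exception can reasonably be taken to carry over. Only a clarifying sentence is needed.

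Finally, SAP 7.4.2 and parts of Protocol section 14 (14.3.3, 14.3.4, 14.7 and the content of 14.10) cannot be read in the public copy and may hold sensitivity analyses. Those would not alter the rule in 7.4.3.

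None of this supplies a reason to impute a questionnaire or test score for someone who has died.

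**Conclusion.** The point holds as one about how the outcome is defined. The readable plan imputes month 12 results after death for endpoints 3 to 7 and allows a death to be counted as a clinically significant improvement in endpoints 5 to 7. It is not a finding of inflated type I error, nor a defect in the primary endpoint.

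The practical size is modest and conditional. At N = 90 with assumed rates of 35% and 15%, moving from the SAP rule to a −1 score lowers the chance of passing by 7 points for one death (74% to 67%) and 22 points for three (74% to 52%). Nearly all of that reflects the decision to count death as unfavourable. With no deaths in the English-language subset nothing changes, and with few deaths it matters only near the significance boundary. Death counts, response rates and subset size are assumptions, and confidence is medium because some sections cannot be read.

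**What to change.** Before database lock, replace the single exception in SAP 7.4.3 with a rule by endpoint:

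- Limit multiple imputation to subjects who are alive at the assessment but have missing data.
- Endpoints 5 to 7: score a death before the 12-month assessment as −1 in the primary analysis. The three-category outcome already has a place for it. Add a sensitivity analysis that excludes deaths.
- Endpoints 3 and 4: impute no score after death, and report the number of deaths beside the result.
- As a clarification only, state that the seizure-related-death exception also covers endpoints 1, 2 and 8, in line with SAP 7.5.

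The cost is a few sentences of SAP text and one extra sensitivity analysis, with no new data. The 89% power stated for the primary endpoint is untouched, because its handling does not change. The downside is that deaths unrelated to epilepsy or the procedure also count against endpoints 5 to 7, so those results may be slightly less favourable; the sensitivity analysis shows by how much.
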